## 11. DATA AND SAFETY MONITORING

Adverse event lists, guidelines, and instructions for AE reporting can be found in **Section 7.0** (Adverse Events: List and Reporting Requirements).

### 11.1 Data Management

All information will be collected on study-specific case report forms (CRFs) by study staff. These data will be reviewed for completeness and accuracy by the Principal Investigator as well as the Sidney Kimmel Comprehensive Cancer Center Clinical Research Office.

#### Protocol Chair

The Protocol Chair is responsible for performing the following tasks:

- Coordinating, developing, submitting, and obtaining approval for the protocol as well as its subsequent amendments.
- Assuring that all participating institutions are using the correct version of the protocol.
- Taking responsibility for the overall conduct of the study at all participating institutions and for monitoring the progress of the study.
- Reviewing and ensuring reporting of Serious Adverse Events (SAE)
- Reviewing data from all sites.

#### Coordinating Center

The Coordinating Center is responsible for performing the following tasks:

- Ensuring that IRB approval has been obtained at each participating site prior to the first patient registration at that site, and maintaining copies of IRB approvals from each site.
- Managing central patient registration.
- Collecting and compiling data from each site.
- Establishing procedures for documentation, reporting, and submitting of AE's and SAE's to the Protocol Chair, and all applicable parties.
- Facilitating audits by securing selected source documents and research records from participating sites for audit, or by auditing at participating sites.

#### Participating Sites

Participating sites are responsible for performing the following tasks:

- Following the protocol as written, and the guidelines of Good Clinical Practice (GCP).
- Submitting data to the Coordinating Center (at the request of the Coordinating Center and the frequency dependent on the rate of subject accrual and the progress of the study).
- Registering all patients with the Coordinating Center by submitting patient registration form, and signed informed consent promptly.
- Providing sufficient experienced clinical and administrative staff and adequate facilities and equipment to conduct a collaborative trial according to the protocol.

- Maintaining regulatory binders on site and providing copies of all required documents to the Coordinating Center.
- Collecting and submitting data according to the schedule specified by the protocol.

## 11.2 Safety Meetings

Scheduled meetings will take place weekly and will include the protocol principal investigator, study coordinator(s), data manager(s), sub-investigators (as appropriate), collaborators (as appropriate), and biostatisticians (as appropriate) involved with the conduct of the protocol. During these meetings, matters related to the following will be discussed: safety of protocol participants, validity and integrity of the data, enrollment rate relative to expectation, characteristics of participants, retention of participants, adherence to protocol (potential or real protocol violations), data completeness, and progress of data for objectives.

## 11.3 Monitoring

Interim analysis of toxicity, outcome and ongoing scientific investigations will be performed every 6 months by the Sidney Kimmel Comprehensive Cancer Center Data Safety Monitoring Board (SKCCC DSMB). The SKCCC DSMB will review aspects of this trial that are outlined in the responsibilities section of the Data and Safety Monitoring Board (DSMB) Guidance. If the committee decides that amendments should be made to this trial, recommendations will be made in writing to the Study Principal Investigator. The study team will submit modifications to the IRB within 60 days of receipt from the DSMB. The Associate Director of Clinical Research, will arbitrate any disagreements between the DSMB and the study Principal Investigator. These changes may include early termination of accrual if deemed appropriate.

Johns Hopkins SKCCC: The protocol will be monitored externally by the SKCCC CRO in accordance with SKCCC guidelines. Trial monitoring and reporting will be done through the Safety Monitoring Committee (SMC) at SKCCC.

Participating site(s): The protocol will be monitored by the internal CRO at each site. A report of the reviews will be submitted to the Johns Hopkins principal investigator and SKCCC CRO.

Authorized representatives of the Coordinating Center may visit the satellite sites to perform audits or inspections, including source data verification. The purpose of these audits or inspections is to systematically and independently examine all trial-related activities and documents to determine whether these activities were conducted and data were recorded, analyzed, and accurately reported according to the protocol, Good Clinical Practice (GCP), and any applicable regulatory requirements.

The Medical Expert Committee (MEC) for this clinical study contains three medical oncologists (see below) from other disciplines who are not affiliated with this clinical trial protocol. The MEC will review safety data on at least a semi-annual basis. The MEC

will provide a written summary of each assessment to the IND Sponsor after each meeting. In turn, the study team will forward these summaries to the JHU IRB, and JHU SKCCC SMC. The operating plan of the MEC will be as follows:

- Meetings will be held at least semi-annually, and potentially more frequently if needed.
- Meetings will be conducted in-person or via video/teleconference, with a participant sign-in sheet collected at each meeting.
- Approximately one week prior to each MEC meeting, the study team will submit the following items to MEC personnel for review and discussion at the meeting (The PI may join the MEC meeting in order to answer any questions the MEC might have):
  - A summary of the clinical trial's progress to date;
  - The latest IRB-approved consent document; and,
  - A summary of all adverse events, serious adverse events, deaths, and withdrawals to date.

Note that the MEC reserves the right to halt trial accrual or all study activity if, after review, serious safety concerns warrant this action. If the MEC halts study accrual or all study activity, then the study team must notify the JHU SKCCC SMC, JHU IRB, and the FDA immediately.

[name] will be holding the IND for this study. He will comply with all regulated reporting requirements to the FDA.

## 12. STATISTICAL CONSIDERATIONS

### 12.1 Study Design and Endpoints

This pilot study is a single dose level assessment of the immunologic response as well as the safety and tolerability of administering TA-CIN vaccine via different sites in patients who have a history of HPV16-related cervical cancer. The primary goal is to determine the most favorable injection site for TA-CIN that exhibits the greater HPV-specific immunogenicity. The secondary goal is to evaluate the safety and tolerability profile of TA-CIN in HPV16 related cervical cancer patients.

The primary endpoint is the immune response rate at the time of the fourth follow-up measurement. The measure of immune response to the regimen will be the antigen-specific T cell response, the simulation index of T cell proliferation, and the titer of the antibody response in peripheral blood. Each patient will have one measurement at baseline and 4 measurements at 4 time points after treatment. For each individual patient, a significant immunologic response is defined as the maximum increase in antigen-specific T cell number or proliferation index after administration of TA-CIN by greater than 1.8 times the standard deviation (SD) of the baseline values, and the increase is at least 2-fold. An increase by 1.8 SD establishes a statistically significant reduction at the two-sided .10 level.

This study will evaluate two different sites, thigh and arm, for TA-CIN vaccine administration.

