### 12.2 Sample Size

A total of 15 patients with a history of advanced HPV16-related cervical cancer will be enrolled and randomized at 1:1 ratio to receive TA-CIN administrations via thigh (Group A) or arm (Group B). Each group will treat at most 7 patients. A previous study by Smyth *et al.* in non-cancer patients who did not receive chemo/radiotherapy showed that 9 out of 25 patients had a detectable E6/E7-specific T cell response one month after TA-CIN vaccination. It is expected that the prior chemo/radiotherapy received by the cervical cancer patients enrolled on this study will prime the response to the TA-CIN such that the T cell response rate will be higher. If the true response rate is 65% for Group A and 45% for Group B, with 7 patients each group, there is about 70% chance of picking the correct injection site based on the observed number of responders in the two groups. Even if the true response rate is 60% for Group A and 45% for Group B, with 7 patients each group, there is still about 60% chance to correctly pick the winner.

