## **12.5 Statistical Analysis**

Adverse events will be tabulated by type and grade for each dose cohort.

The measure of immune response to the regimen will be the number of antigen-specific T cells detected by ELISPOT and/or ICC, or the simulation index of T cell proliferation, and the titer of the serum antibody as determined by ELISA. Each patient will have one measurement at baseline and 5 measurements at 5 time points after treatment. Descriptive statistics (mean and SD) and box plots will be used to summarize the immunogenicity by time point and dose cohort. Formal hypothesis testing will not be conducted to determine the ideal vaccination site. Instead, a “winner” will be picked based on the observed number of responses (42). Two-sample t-test will be used to compare the immunogenicity between two immunization sites. Data transformation will be applied if the distribution is not normal. In addition, the time course of outcomes will be investigated graphically by individual subject plots.

Cox regression analysis will be conducted to explore the association between time to disease recurrence and vaccine-induced immune response status. Patient baseline characteristics including disease stage and history of treatment will be adjusted in the analysis.

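### Section 12.1: the responder rule behind the primary endpoint cannot be tied to one visit, and the two-sided .10 level attached to 1.8 SD is not a property of that rule

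*Combined protocol and SAP*

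**What the plan says.** - **Endpoint (Section 12.1).** "The primary endpoint is the immune response rate at the time of the fourth follow-up measurement".
- **Responder (Section 12.1).** Responder status is "defined as the maximum increase in antigen-specific T cell number or proliferation index after administration of TA-CIN". To count, that rise must exceed the patient's baseline "by greater than 1.8 times the standard deviation (SD) of the baseline values, and the increase is at least 2-fold".
- **Level (Section 12.1).** "An increase by 1.8 SD establishes a statistically significant reduction at the two-sided .10 level".
- **Measurements.** Section 12.1: "Each patient will have one measurement at baseline and 4 measurements at 4 time points after treatment". Section 12.5: "Each patient will have one measurement at baseline and 5 measurements at 5 time points after treatment". The Section 10 calendar schedules T cell blood at pre-study and then at Week 5, Week 9, Weeks 11-13 and Months 6, 12 and 24.
- **Use.** Under Section 12.5 the winning injection site "will be picked based on the observed number of responses", and no formal hypothesis test is to decide the site.
- **Readouts.** Section 1 puts ELISPOT first, then T cell proliferation or ELISA antibody if ELISPOT does not discriminate. Section 12.1 joins T cell number and proliferation index with an 'or'. It lists antibody titer among the measures but leaves it out of the responder definition.

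**The concern.** The responder count is the primary endpoint of Section 12.1 and the quantity that selects the site, so the rule must give one answer for each patient. As written, two analysts with the same data could choose different visits, or one could take the value at a visit and the other the best value up to it. They could then report different counts.

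The sentence about the level makes this harder to see, because it suggests the threshold has a known false-positive rate. It speaks of a reduction where the rule concerns an increase. It relies on an SD of baseline values when each patient has one baseline measurement. It also attaches a level to 1.8 SD when the rule in use involves a maximum over visits, two readouts and a 2-fold condition.

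**Working it through.** **1. Which visit is the fourth?**

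| Counting rule | T cell draws, in order | Number | Fourth |
|---|---|---|---|
| After dose 1 (Week 1) | Weeks 5, 9, 11-13; Months 6, 12, 24 | 6 | Month 6 |
| After dose 3 (Week 9) | Weeks 11-13; Months 6, 12, 24 | 4 | Month 24 |

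The second row matches the 4 in Section 12.1. Neither row gives the 5 in Section 12.5. The planning reference in Section 12.2 "showed that 9 out of 25 patients had a detectable E6/E7-specific T cell response one month after TA-CIN vaccination". If that means one month after the last dose, the nearest draw here is Weeks 11-13, which is neither candidate.

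**2. At the visit, or best through it?** Take a patient who meets both conditions at Weeks 11-13 and has fallen back by Month 6. She is a responder on the best-response reading and a non-responder at Month 6. A patient who first meets them at Month 12 is a non-responder on either Month 6 reading, but a responder on best response through Month 24.

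**3. How much can one patient matter?** With 7 per group, one changed status moves a group's rate by 1/7 = 14 percentage points. Let X_A and X_B be binomial with n = 7.
- At 65% v 45%, P(X_A > X_B) = .693, which agrees with the plan's figure of about 70%. P(tie) = .158.
- At 60% v 45%, P(X_A > X_B) = .621, against the plan's figure of about 60%. P(tie) = .179.
- Summing the joint probabilities with |X_A − X_B| ≤ 1 gives .457 and .506. In about half of such trials, one reclassified patient can make or break a tie.

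**4. Can the stated .10 be reproduced?**
- Normal deviate of 1.8: 2(1 − Φ(1.8)) = .072. A two-sided .10 needs 1.645.
- One new value against the mean of n baselines: 2P(t(n−1) > 1.8/√(1 + 1/n)) = .106 at n = 14 and .103 at n = 15. This is close to .10, but it compares a value with a cohort mean, whereas the rule uses a patient's own increase.

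**5. What is the level for one patient's own difference?** Let ρ be the correlation between baseline and follow-up on the scale of the SD used. The difference has SD √(2(1 − ρ)) in those units, so the two-sided level is 2(1 − Φ(1.8/√(2(1 − ρ)))).

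| SD used | ρ | 1.8/√(2(1 − ρ)) | Two-sided level |
|---|---|---|---|
| Known within-patient SD, independent errors | 0 | 1.273 | .203 (one-sided .102) |
| Across-patient SD | .25 (assumed) | 1.470 | .142 |
| Across-patient SD | .40 (assumed) | 1.643 | .100 |
| Across-patient SD | .50 (assumed) | 1.800 | .072 |
| Across-patient SD | .80 (assumed) | 2.846 | .004 |

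With one baseline per patient, the planned visits supply only the across-patient SD. It mixes differences between patients with variation within a patient, so it fixes no error level for one patient's change. The documents give neither an SD nor a correlation.

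**6. What about the full rule? (illustration only)** Assume a log scale, no vaccine effect, one readout, K visits and within-patient ln-SD s. The false-responder rate is 1 − E[Φ(c + e)^K], with e standard normal and c = max(1.8, ln 2/s).
- K = 4: .024, .147 and .262 at s = 0.2, 0.3 and 0.4.
- K = 6, s = 0.4: .32.
- Two independent readouts, K = 4, s = 0.4: 1 − (1 − .262)² = .455.

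The rate can fall well below or well above .10, depending on inputs the documents do not give.

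**The case against.** **The level is nearly right.** The rule counts increases only, and the one-sided level for a single difference with a within-patient SD is .102, so the error may be just the label two-sided. The comparison with a cohort mean also gives .103 to .106. This stands as an explanation of where .10 may have come from. It does not rescue the sentence, because the first reading needs an SD that the planned visits cannot supply and the second is not the rule.

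**The sentence claims no level for the full rule.** Literally, it speaks only of an increase of 1.8 SD. That is fair, but the sentence directly follows the rule and is the only error rate given for it, so a reader will take it as the rule's level.

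**Nothing formal depends on it.** This stands. No test of site uses the level, and it does not enter the 70% and 60% selection figures.

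**The readout order exists.** Section 1 gives one, and the two sections can be read together. What is missing is a definition of when ELISPOT fails to discriminate, a choice between the later steps, and the carry-over into Section 12.

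**Stronger readings to avoid.** A reader might infer that the true level is .203, twice the stated one. That holds only for a known within-patient SD with independent errors, and the documents identify no such SD. A reader might also infer that false responders cut the chance of a correct pick, for example from .693 to .624 at 65% v 45% if 26.2% of true non-responders are misclassified in each group. That requires an assumed SD and planning rates that exclude false responders. If the Section 12.2 rates are rates of being classified a responder, which is a natural reading, nothing is lost. These figures are also not worst cases, since six visits or two readouts give higher rates.

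**Conclusion.** The point holds, and the plan should be corrected.

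- **Visit.** This rests on the text alone. The follow-up counts are 4, 5 and 6, the fourth measurement is Month 6 or Month 24, and judging at the visit or as best response through it are both open. The responder count, and so the site picked, can differ between readings of the same data.
- **SD and level.** The SD source is not stated, and a two-sided .10 is not a property of the rule. Even for a single difference the level runs from .203 down to .004 across the SD readings and assumed correlations shown. No level for the full rule can be derived from the documents.
- **Wording.** Reduction contradicts increase within one sentence.
- **Readout.** This is mainly missing detail.

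The practical weight lies in the visit and the SD source. The level sentence misdescribes the threshold but changes no planned calculation. The Laboratory Manual, to which the protocol refers for specimen handling, was not available. If it provides replicate baselines, the SD point would need to be read with it.

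**What to change.** 1. **Level.** Delete the sentence on the .10 level and claim no error level for the rule. A one-sided level of about .10, for one follow-up-minus-baseline difference only, could be stated if there is a within-patient SD that includes visit-to-visit variation. An assay SD alone would not support it.
2. **SD.** State that the SD is across patients unless replicate baselines exist. Keep the 2-fold criterion.
3. **Visit.** Name the endpoint visit by calendar time. Say whether response is judged at that visit or is the best response through it. Make the counts in Sections 12.1 and 12.5 agree with the Section 10 calendar.
4. **Readout.** Carry the Section 1 order (ELISPOT, then proliferation or antibody) into Section 12.1, define the trigger for moving on, and say whether antibody can make a patient a responder.

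Settle all four before responders are counted, so that the choice cannot follow the data. The cost is wording in Sections 12.1 and 12.5, with no new visits, samples or patients. The downside is that the stated error level is withdrawn.

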### 12.2 Sample Size

A total of 15 patients with a history of advanced HPV16-related cervical cancer will be enrolled and randomized at 1:1 ratio to receive TA-CIN administrations via thigh (Group A) or arm (Group B). Each group will treat at most 7 patients. A previous study by Smyth *et al.* in non-cancer patients who did not receive chemo/radiotherapy showed that 9 out of 25 patients had a detectable E6/E7-specific T cell response one month after TA-CIN vaccination. It is expected that the prior chemo/radiotherapy received by the cervical cancer patients enrolled on this study will prime the response to the TA-CIN such that the T cell response rate will be higher. If the true response rate is 65% for Group A and 45% for Group B, with 7 patients each group, there is about 70% chance of picking the correct injection site based on the observed number of responders in the two groups. Even if the true response rate is 60% for Group A and 45% for Group B, with 7 patients each group, there is still about 60% chance to correctly pick the winner.

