## 1. SUMMARY

This is a randomized, multi-center, open label pilot study. The primary goal of this study is to determine the safety of TA-CIN vaccine as adjuvant therapy, and to assess evidence of induction of HPV antigen-specific immunologic response when administered at different locations. TA-CIN has proven to be well-tolerated in healthy humans when administered three times monthly intramuscularly in the deltoid at a 533 $\mu$ g dose. In this pilot study, a single dose level (100 $\mu$ g) assessment of the safety and tolerability of administering TA-CIN vaccine three times to either the arm versus the thigh of patients who have previously been treated for HPV16-related cervical cancer in the past year and are documented to have no evidence of disease recurrence based on standard-of-care imaging and/or clinical assessment upon eligibility. Since TA-CIN administration is likely to have low toxicity, an important element of this study is to analyze immunologic parameters to examine whether one of the two immunization sites induces greater HPV-specific immunogenicity. The immunogenicity analyses include: 1) assessment of T cell-mediated immune responses of peripheral blood lymphocytes to HPV16 E7E6 stimulation by ELISPOT, and if not discriminatory then 2) by T cell proliferation assays, or 3) by measurement of HPV16 L2E7E6-specific antibodies by ELISA (**Section 10**). These analyses will be combined with toxicity data to select a vaccination site for a future clinical trial(s).

A total of 15 patients will be enrolled to assess the safety of TA-CIN vaccine via different injection sites as adjuvant therapy. Patients with HPV16-associated stage IB1-IV cervical cancer who completed definitive cancer treatment within 1 year before the initiation of vaccination and are documented to have no evidence of disease recurrence based on standard-of-care imaging and/or clinical assessment will be eligible. This population was chosen because women with HPV-associated cervical cancer may potentially benefit from the vaccination strategy as adjuvant therapy as compared to healthy volunteers with respect to prevention or delay in the development of HPV16 associated cervical cancer recurrence. One dose level of TA-CIN (100 $\mu$ g) delivered via one of two different intramuscular injection sites is planned (**Section 6**).

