Safety assessments will continue for a period for 1 month after the last vaccination; reporting requirements, exclusions, and stopping rules are outlined (**Sections 7 and 8**). Subjects who withdraw from the study for reasons other than toxicity may be replaced at the discretion of the Principal Investigator and/or IND sponsor.

Few or no serious adverse events (SAEs) are expected from this regimen and routes of administration. The motivation for the design is to confirm that the dose and site of injection implemented here has minimal or no systemic toxicity, as well as determining the preferred injection site that can elicit more potent immune response.

Patient immune and clinical responses in cohorts with different injection sites will be evaluated through the following methods: 1) peripheral blood lymphocytes (PBL) to assess HPV16 E6 and E7-specific CD8 $^{+}$  T cell ELISPOT and lymphocyte proliferative responses to HPV16 antigenic stimulation and T cell receptor sequencing; 2) serum for HPV16 L2, E6, and E7 and neutralizing antibody responses; 3) plasma for residual HPV viral load; and, 4) imaging scans per standard-of-care (i.e., every 6-12 months) and as clinically indicated to assess time to disease recurrence.

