### 12.4 Early Stopping Rules

This study will evaluate two different sites of TA-CIN vaccine to determine the safety

and effectiveness of TA-CIN in patients with a history of advanced cervical cancer. For each injection site, the SAE rate of 20% or more is deemed unsafe. A total of 15 patients will be enrolled, with 7-8 patients in each injection site cohort.

The study will be stopped early if there are more than two patients with SAEs observed during the study. If the SAE rate is 20% or more, there is at least 55% chance to stop the study early with 15 patients.

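### Group sizes conflict, and the site is picked on a raw number of responders although the endpoint is a rate; the stated selection chances hold only for exactly 7 v 7 with ties counted as not correct

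*Combined protocol and SAP*

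**What the plan says.** Section 12.1: "The primary endpoint is the immune response rate at the time of the fourth follow-up measurement".

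Section 12.2 enrols 15 patients at 1:1 and adds: "Each group will treat at most 7 patients". With 7 per group and true rates of 65% (Group A, thigh) and 45% (Group B, arm), "there is about 70% chance of picking the correct injection site based on the observed number of responders in the two groups". For 60% v 45% it gives about 60%.

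The Schema table and the Section 6.3 table both show 7 patients per site. Section 12.4 says: "A total of 15 patients will be enrolled, with 7-8 patients in each injection site cohort".

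Section 12.5 rules out formal testing for the choice of site; instead a winner "will be picked based on the observed number of responses".

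Section 1 has the nearest thing to a tie-breaker. ELISPOT comes first, "and if not discriminatory then 2) by T cell proliferation assays", or by antibody, and the results are to be combined with toxicity data. It also says that patients who withdraw for reasons other than toxicity "may be replaced at the discretion of the Principal Investigator and/or IND sponsor".

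**The concern.** Two groups capped at 7 hold at most 14 patients, so the cap, the tables, the total of 15 and the 7-8 range cannot all describe the same patients. This matters because a raw number of responders is a fair yardstick only when the groups are equal. With one extra patient a group has one more chance to score, whichever site is better. Section 12 does not say whether the pick is made among randomized, dosed or evaluable patients, or what happens when the results are equal.

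Section 12.1 calls the choice of site the primary goal, and Section 1 carries it into later trials. With no hypothesis test, the selection rule is the whole inferential basis of that choice.

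**Working it through.** **Inputs.** True rates 65/45 and 60/45 (thigh/arm) and 7 per group from Section 12.2; the 7-8 range from Section 12.4.

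**Formula.** With X ~ Bin(n_T, p_T) responders in the thigh group and Y ~ Bin(n_A, p_A) in the arm group, independent:
- correct by count = sum of P(X=x)P(Y=y) over x > y
- tied = the same sum over x = y
- wrong = the same sum over x < y
- for the proportion rule, compare x/n_T with y/n_A instead.

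**Reproducing the plan's figure (7 v 7, 65/45).** P(X = 0,...,7) = 0.0006, 0.0084, 0.0466, 0.1442, 0.2679, 0.2985, 0.1848, 0.0490. P(Y = 0,...,7) = 0.0152, 0.0872, 0.2140, 0.2918, 0.2388, 0.1172, 0.0320, 0.0037.
- Tied: 0.0000 + 0.0007 + 0.0100 + 0.0421 + 0.0640 + 0.0350 + 0.0059 + 0.0002 = 15.8% after rounding.
- Correct, summing P(X=x)P(Y≤x−1) for x = 1 to 7: 0.0001 + 0.0048 + 0.0456 + 0.1629 + 0.2528 + 0.1782 + 0.0488 = 69.3%.
- Wrong: 100 − 69.3 − 15.8 = 14.9%.

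At 60/45 the same sums give 62.1% correct, 17.9% tied and 20.0% wrong. Both stated figures are therefore sound on the unstated convention that a tie is not a correct pick. With ties split evenly they become 69.3 + 15.8/2 = 77.2% and 62.1 + 17.9/2 = 71.1%.

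**The 7/8 splits** (each cell 65/45, then 60/45):

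| Sizes and rule | Correct | Tied | Wrong |
|---|---|---|---|
| Thigh 8, arm 7, count | 79.6% / 72.8% | 11.5% / 14.1% | 8.9% / 13.1% |
| Thigh 8, arm 7, proportion | 79.6% / 72.8% | about 0 | 20.4% / 27.2% |
| Thigh 7, arm 8, count | 60.0% / 52.6% | 18.0% / 19.4% | 22.0% / 28.0% |
| Thigh 7, arm 8, proportion | 78.0% / 72.0% | about 0 | 22.0% / 28.0% |

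**Equal true rates of 45%, 7 v 8.** By count the larger group wins 48.9%, the smaller 31.2%, and 19.9% are tied. By proportion the split is 48.9% larger and 51.0% smaller.

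**Where the two rules part.** Let the groups have n and n+1 patients with x and y responders. If y > x then y ≥ x+1, and (x+1)/(n+1) ≥ x/n because x ≤ n; so the larger group is never behind on proportion when it leads on count. If x > y, the smaller group leads on both. Opposite winners are impossible at a one-patient imbalance. In practice the rules differ only at equal counts, which the count rule leaves open and the proportion rule gives to the smaller group (4/7 beats 4/8). With the arm at 8 that is the whole gap: 60.0 + 18.0 = 78.0%. With the thigh at 8 the same mechanism adds wrong picks: 8.9 + 11.5 = 20.4%.

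**An imbalance of two (illustration, thigh 6 v arm 8).** Here 4/6 beats 5/8 on proportion but loses on count. The rules name opposite winners in 7.5% / 6.7% of outcomes.

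**The Section 1 fallback.** It does not define when an assay is not discriminatory, and Section 12.5 does not carry it. The responder definition in Section 12.1 already accepts a rise in T cell number or in proliferation index, so moving on to proliferation need not break a tie. That definition has no antibody criterion.

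**The case against.** The best defence is that Section 12.2 does state 7 per group, that count and rate are then the same rule, and that its arithmetic is right. Fifteen enrolled and 14 treated could be squared by one replacement (Section 1) or one cancelled registration (Section 5.1). Section 2.1 names safety and feasibility as the only primary objective, Section 1 makes the choice a combined immune and toxicity judgement, and Section 12.5 also plans a two-sample t-test of immunogenicity between sites.

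Much of this stands. It does not remove the conflict: no section says that the 15th patient is a replacement, the 7-8 range contradicts a cap of 7, and ties remain even at 7 v 7. Section 12.5 does not link the t-test to the pick.

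Three stronger readings are tempting, and the documents do not support them.
- A reader might infer that the 70% and 60% are miscalculated. They are not.
- A reader might infer that with 15 patients the count rule often names a different winner from the rate. At 7 v 8 it never does. Opposite winners need an imbalance of two evaluable patients, and the documents give no attrition rate. Section 10 leaves research sampling to the PI's discretion for supply and safety reasons, which makes losses possible but does not show that they are expected.
- A reader might infer that nothing at all is provided for ties. Section 1 offers an ordered assay fallback; the fault is that it is undefined and absent from Section 12.5.

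Nor is the 78.0% against 60.0% at thigh 7 v arm 8 a pure gain in accuracy. It mostly compares ties left open with ties handed to the smaller group.

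**Conclusion.** The point holds in this form: the group sizes cannot all be followed, the selection rule does not match the endpoint, and the stated chances describe only one of the sizes that the plan allows. With one group at 8, the chance of a correct pick by count ranges from 60.0% to 79.6% (65/45) or from 52.6% to 72.8% (60/45), depending only on which site has the extra patient. Between 11.5% and 19.4% of outcomes across those splits are ties with no working rule. These figures assume independent binomial responses, the plan's own response rates, and every patient evaluable. The issue should be fixed, but it does not undermine the design.

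**What to change.** 1. State one set of group sizes in the Schema table, the Section 6.3 table, and Sections 12.2 and 12.4, and say whether the 15th patient is an extra or a replacement.
2. In Sections 12.2 and 12.5, select on the observed response proportion among patients evaluable for immune response, with evaluable defined before analysis. Show the proportion among all dosed patients as a sensitivity analysis.
3. Put one tie rule into Section 12.5, based on a measure not already in the responder definition, for example the continuous ELISPOT increase or the antibody titre. Apply it also to equal responder counts when the groups differ by one patient, so that the smaller group does not win automatically.
4. Restate correct, tied and wrong chances for the final sizes and the rule adopted. At 7 v 7 these are 69% / 62% correct with ties not counted, or 77% / 71% with ties split. At 7 v 8 by pure proportion they are 78-80% / 72-73% correct and 20-22% / 27-28% wrong. If equal counts go to the tie measure instead, the direct picks at 7 v 8 are in effect those in the count rows of the table, with the tied share settled by that measure.

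Two limits should be stated openly. The pure proportion rule gives more wrong picks than the count rule when the better site has the larger group. With item 3 in place, a 7/8 split still leaves some dependence on group size, which only equal groups remove.

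The cost is wording in three sections and two tables, with no added patients, visits or assays.
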